8.6. Replacement of Subjects

If a subject withdraws or is withdrawn from the study at the discretion of the investigator or DMC up to and including the Week 12 visit, the subject may be replaced with another subject meeting the eligibility criteria. The replacement subject will receive the same treatment assignment as the replaced subject. Up to 10 subjects total may be replaced. Refer to Section 7 and Section 10.1 for details about treatment assignments and randomization. Refer to Section 8.5 for guidelines on study drug dose reduction, withholding, and discontinuation and to Section 8.4 for guidelines on withdrawal of subjects from study participation. All data collected prior to withdrawal must be recorded in the replaced subject's eCRF.

8.7. Stopping Rules and Study Termination

It is anticipated that AEs will occur frequently in this population based on the underlying disease, and that these can also be SAEs. There is no predefined type or frequency of AEs or SAEs for a stopping rule in this study. Review of SAEs and deaths on study will be performed routinely by the DMC, as defined in this protocol and in the DMC charter.

If a safety concern arises that warrants review for possible study termination, the DMC (or party identifying such concern) will notify the sponsor immediately. Enrollment in the study may be temporarily halted for further review of safety data. This further assessment of safety data will include review by the DMC, which may include the recommendation to terminate the study early, as outlined in the DMC charter.

Termination of the clinical study may also occur due to a regulatory authority decision or if the sponsor or regulatory authority decides that subject safety may be compromised by continuing the study.

If the study is halted temporarily or prematurely terminated, a written statement fully documenting the reasons for study halt or termination will be provided to the Institutional Review Board (IRB)/ Independent Ethics Committee (IEC) and appropriate regulatory authorities.

9. STUDY TREATMENTS

9.1. Study Drug

Study drug (IMR-687 or placebo) is to be taken as 2 tablets orally qd.

IMR-687 will be supplied as 100, 150, or 200 mg white tablets. To optimize dosing, 60 kg will be used as the body weight gate for the administered tablet strength. Subjects in the lower dose group weighing <60 kg will be dispensed 100 mg tablets, and those weighing \geq 60 kg will be dispensed 150 mg tablets. Subjects in the higher dose group weighing <60 kg will be dispensed 150 mg tablets and those weighing \geq 60 kg will be dispensed 200 mg tablets. The different doses of IMR-687 are visually identical in tablet form.

Placebo will be supplied as white tablets containing matrix absent IMR-687. The placebo tablets are visually identical to the IMR-687 tablets.

Subjects will be directed to take study drug (either IMR-687 or placebo) with food, but if a subject does not do so, it will not be considered a protocol deviation.

9.2. Packaging and Labeling

Finished tablets will be packaged in round, 60 cc high-density polyethylene bottles with a polypropylene cap. Each bottle contains 84 tablets. The bottles are induction sealed and capped. Each bottle will be labeled with a suitable Annex 13 country compliant product label.

9.3. Storage Conditions

Upon receipt of the study drug, an inventory must be performed, and a drug receipt log completed and signed by the person accepting the shipment. It is important that the designated study staff counts and verifies that the shipment contains all the items noted in the shipment inventory.

Only subjects enrolled in the study may receive study drug, and only authorized site staff may supply or administer study drug to subjects. All study drug must be stored in a secure, environmentally controlled, and monitored (manual or automatic) location in accordance with the labeled storage conditions and with access limited to the investigator and authorized site staff.

The study site must maintain accurate records demonstrating dates and quantity of study drug received, to whom dispensed (subject-by-subject accounting), any amount returned, and accounts of any study drug that was accidentally destroyed.

9.4. Administration

Subjects will be advised to take 2 tablets (IMR-687 or matched placebo) orally qd during the treatment period. Subjects will be directed to take their study drug with food. On days when study drug is taken in the clinic, food details will also be recorded.

9.5. Treatment Compliance

The investigator or designee must ensure that all subjects are adequately informed of study drug administration requirements for compliance/adherence with the study protocol.

Treatment compliance/adherence with scheduled oral administration of study drug will be assessed at the study site starting at Week 4; all study drug administration will be documented on the appropriate pages of the eCRF. Subjects falling below an 80% treatment compliance rate between consecutive visits will be reported as a protocol deviation.

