8.5. Guidelines for Study Drug Dose Withholding or Discontinuation

In consultation with the medical monitor, the investigator may decide to withhold or discontinue study drug dosing in cases where tolerability or safety concerns emerge. [Table 2](#) provides recommended guidelines for these decisions.

If a study drug dosing is withheld due to an AE (Section [12](#)), subjects who continue on the study will have all assessments (except study drug administration) performed as per protocol.

If study drug dosing is discontinued for any reason, the specific circumstances surrounding the discontinuation must be recorded in the subject's eCRF. Any subject who discontinues study drug dosing must also be withdrawn from the study; however, all appropriate safety assessments and follow-up should be completed prior to withdrawal (Section [8.4](#)).

Table 2: Safety Guidelines for Study Drug Dose Reduction, Withholding, or Discontinuation

Dose Reduction	
Event	Recommended Action
A Grade 2 or higher TEAE that, in the opinion of the investigator, is both study drug related and that makes continued dosing at the current dose level inadvisable due to safety concern or lack of tolerability.	
Study drug may be reduced by 1 tablet for up to 14 continuous days.
 
If, in the opinion of the investigator, a longer dose reduction is clinically needed, the medical monitor should be contacted.
 
If, in the opinion of the investigator, the severity of the Grade ≥ 2 TEAE has reduced to Grade ≤ 1, the subject may resume study drug at the original dose. If the TEAE recurs after re-introduction of the original dose, the subject should be withdrawn from the study.

Dose Interruption (Hold)	
Event	Recommended Action
A Grade 3 or higher TEAE that, in the opinion of the investigator, is both study drug related and that makes continued dosing at the current dose level inadvisable due to safety concern or lack of tolerability.	
Study drug should be held for up to 7 continuous days until reduction in severity of the TEAE to Grade ≤ 2, then resumed at the original dose.
 
If, in the opinion of the investigator, dosing should be resumed at a lower dose, the medical monitor should be contacted.
 
If, in the opinion of the investigator, a longer dose hold is clinically needed, the medical monitor should be contacted or the subject should be withdrawn from the study.

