Positive test results for COVID-19 and/or similar illness (asymptomatic and symptomatic).	Study drug should be held until 7 days after subject tests negative. Please consult with the medical monitor if there are any questions regarding when to resume study drug.

Abbreviations: COVID-19 = coronavirus disease 2019; TEAE = treatment-emergent adverse event.

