11.6 Per Protocol Analysis Set

The per protocol (PP) analysis set will include all subjects in the safety analysis set who had at least 1 VOC in the 12 months prior to randomization, completed at least 1 valid clinical outcomes assessment without major protocol deviations or events that would be expected to affect the analysis and did not discontinue prior to Week 24 for reasons other than AEs. Subjects will be analyzed according to the actual treatment they received. The PP set will be used for sensitivity analyses of efficacy, PD, and clinical outcome parameters.

Major protocol deviations and subjects (or data) excluded from the PP Analysis Set will be defined by the Sponsor in a blinded manner prior to database lock.

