13.3 Exposure and Drug Accountability

A summary of exposure and compliance, to be reported on the safety analysis set, will include the total number of tablets taken, compliance (%), total exposure (mg), average daily dose (mg/day), duration of exposure (in weeks), and incidence and duration of dose interruption. These parameters will be calculated as follows:

- Duration of exposure (in weeks) will be calculated as [(date of last dose of study medication – date of first dose of study medication + 1)/7]. The date of first dose of study medication will be collected from the Study Drug Administration CRF page and the date of last dose of study medication will be collected from the End of Treatment CRF page. If there is no date for end of treatment on the End of Treatment CRF page, the last available dose date will be used. See Appendix 4 for a complete set of data handling rules.
- Total number of tablets taken = total number of tablets dispensed – total number of tablets returned. The total number of tablets dispensed and returned will be collected from study drug accountability CRF Page. They are to be collected at study visits and will be summed over the whole study treatment period.
- Total exposure (mg) of IMR-687 = Total number of tablets taken * tablet dose level (100/150/200 mg). IMR-687 will be supplied as 100, 150, or 200 mg white tablets in the study. In the lower dose group (≥ 3.0 to ≤ 4.5 mg/kg), subjects weighing <67 kg will be dispensed 100 mg tablets and those weighing ≥ 67 kg will be dispensed 150 mg tablets. In the higher dose group (4.5 to ≤ 6.7 mg/kg), subjects weighing <67 kg will be dispensed 150 mg tablets and those weighing ≥ 67 kg will be dispensed 200 mg tablets. The dose regimen for all subjects is 2 tablets once daily. The weight

at the baseline will be used to establish the dose level and the same dose level will be used throughout the trial.

- Incidence and duration of dose interruption: as collected from the IP Interruptions CRF page.
- Overall compliance (%) = [(total number of tablets dispensed – total number of tablets returned) / duration of exposure (days)] x 100.
- Average daily dose (mg/day) = total exposure (mg) / duration of therapy (days).

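### The 80% compliance rule has no defined denominator and no exception for Table 2 holds and reductions, and the SAP compliance formula omits the two-tablet daily dose

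*Protocol*

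**What the plan says.** Protocol 9.5: "Treatment compliance/adherence with scheduled oral administration of study drug will be assessed at the study site starting at Week 4". It then sets the threshold: "Subjects falling below an 80% treatment compliance rate between consecutive visits will be reported as a protocol deviation". It gives no numerator or denominator and does not refer to Section 8.5.

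Protocol 9.4 sets the schedule: "Subjects will be advised to take 2 tablets (IMR-687 or matched placebo) orally qd during the treatment period".

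Protocol 8.5, Table 2, which is introduced as recommended guidelines, provides for three kinds of omitted dose:
- Reduction for a drug-related TEAE of Grade 2 or higher: "Study drug may be reduced by 1 tablet for up to 14 continuous days".
- Hold for a drug-related TEAE of Grade 3 or higher: "Study drug should be held for up to 7 continuous days", ending when severity falls to Grade 2 or lower.
- Hold for a positive COVID-19 test: "Study drug should be held until 7 days after subject tests negative".

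SAP 13.3 defines overall compliance as tablets dispensed minus "total number of tablets returned) / duration of exposure (days)] x 100". Compliance per dosing period is listed as it comes from the CRF, with no formula.

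SAP 13.2 has an important-deviation category for significant departures in dosing. SAP 11.6 limits the per-protocol (PP) set to subjects with a valid assessment "without major protocol deviations or events that would be expected to affect the analysis", and leaves the definition of a major deviation to the sponsor, blinded, before database lock.

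**The concern.** A compliance threshold should identify subjects who did not take what they were told to take. As written, the rule can also catch a subject who omitted doses because the investigator followed Table 2. Neither document contains an exception. Because the denominator is not defined, sites may also classify identical subjects differently.

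Three outputs could be affected:
- the deviation table, which could show protocol-permitted omissions as non-adherence;
- the PP sensitivity analyses of the primary and key secondary endpoints (SAP 13.5.2.4, 13.5.3.1 and 13.5.3.2.2), if such deviations were classed as major;
- the compliance summary itself, because the SAP formula does not return a percentage of the scheduled dose.

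The PP definition also sits awkwardly with the rule. Stopping drug for an AE before Week 24 does not exclude a subject, but nothing expressly protects one who has a Table 2 hold for an AE and continues.

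**Working it through.** The documents give a threshold but no compliance result, so there is no figure of the plan's own to reproduce.

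**Inputs**
- Daily schedule: 2 tablets (Protocol 9.4).
- Visit intervals: about 28 days to Week 24, 42 days to Week 36, 56 days to Week 52 (Protocol 7.1.2, Table 1).
- Full hold: 7 days × 2 = 14 tablets omitted. Full reduction: 14 days × 1 = 14 tablets omitted (Table 2).

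**Reading A: every calendar day counts.** This is an assumption, since 9.5 does not say so. Compliance = (2D − m)/(2D), where D is interval days and m is tablets omitted. With m = 14:

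| Interval | Tablets | Compliance | Below 80%? |
|---|---|---|---|
| 28 days | 56 | 42/56 = 75.0% | yes |
| 42 days | 84 | 70/84 = 83.3% | no |
| 56 days | 112 | 98/112 = 87.5% | no |

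A full hold equals 80% when (D − 7)/D = 0.80, so D = 35 days. Any shorter interval is flagged. The visit windows matter as well. Weeks 4 and 8 each allow ±5 days, so that interval can run from 18 days (11/18 = 61.1%) to 38 days (31/38 = 81.6%).

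Shorter actions within 28 days fall on either side of the line:
- hold of 5 days: 46/56 = 82.1%; of 6 days: 44/56 = 78.6%
- reduction of 11 days: 45/56 = 80.4%; of 12 days: 44/56 = 78.6%

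It is also unclear which contacts count as consecutive visits. If Week 1 to Week 4 (21 days) is an interval, the full action gives 28/42 = 66.7%. If telephone contacts split intervals to 14 days, a full action gives 14/28 = 50%.

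**Reading B: withheld doses are not scheduled.** The same subject in a 28-day interval scores 42/(56 − 14) = 42/42 = 100%.

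**COVID-19 hold.** No maximum is stated. Taking the hold as days positive plus 7, wholly within one interval, under Reading A:

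| Assumed days positive | Hold | 28 days | 42 days | 56 days |
|---|---|---|---|---|
| 1 | 8 days | 20/28 = 71.4% | 34/42 = 81.0% | 48/56 = 85.7% |
| 4 | 11 days | 17/28 = 60.7% | 31/42 = 73.8% | 45/56 = 80.4% |
| 10 | 17 days | 11/28 = 39.3% | 25/42 = 59.5% | 39/56 = 69.6% |

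**SAP 13.3 formula, applied to 28 days**
- Full adherence as printed: 56/28 × 100 = 200%.
- After a full hold or reduction, as printed: 42/28 × 100 = 150%.
- With the missing factor of 2: 42/(2 × 28) × 100 = 75%.
- Over 52 weeks with that factor: (728 − 14)/728 = 714/728 = 98.1%.

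**The case against.** The strongest case on the other side has six parts.

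1. **One reading of the denominator.** A reader might infer that any subject managed exactly per protocol scores 75% and must be reported. The documents do not support that. Section 9.5 measures adherence to scheduled administration, which can be read as net of a hold. Even under the calendar-day reading, 75% needs the maximum action wholly within one 4-week interval. Table 2 is guidance, its durations are upper limits, and the reduction is permitted rather than directed. This stands, and it makes the missing definition the firmer defect.
2. **The SAP formula covers overall compliance, not the inter-visit rate.** This stands: at 98.1% over 52 weeks, one Table 2 action would not trip an 80% threshold even with the formula corrected. The formula is still wrong as printed.
3. **PP exclusion is not automatic.** A reader might infer that following Table 2 removes a subject from the PP set. Nothing ties the 80% threshold to a major deviation, and the sponsor defines those under blind. This stands: exclusion is possible, not prescribed.
4. **Arm imbalance.** Because AE holds and reductions require drug-related events, a reader might infer that these deviations concentrate in the higher-dose arm. Protocol 4.2.3.1 reports nausea in 35% of fasted single-dose IMR-687 subjects against 0% on placebo, so a tilt is plausible. But food reduced nausea, this study directs dosing with food, and the documents give no frequency of holds by arm. COVID-19 holds have no stated link to arm.
5. **Holds are reported separately.** SAP 13.3 already summarises the incidence and duration of interruptions. This helps a reader of the exposure table but does not change the deviation count.
6. **Timing.** SAP 8.1.1 puts the last randomization in August 2021, so the 4-week intervals (to Week 24) ended by about late February 2022, before the SAP of 1 March 2022. A protocol edit cannot act prospectively on them. The classification of logged deviations and the SAP derivation can still be corrected.

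**Conclusion.** The concern holds in a limited form. Section 9.5 attaches a reportable consequence to a rate it does not define and does not except Table 2 actions. The two available readings give 75% and 100% for the same subject, on opposite sides of the threshold. Under the calendar-day reading, the outcome of an identical full-length action also depends on the visit calendar: 75% before Week 24, then 83.3% or 87.5%. A COVID-19 hold might look as if it is always flagged, but that rests on one assumed duration; in the longer intervals it depends on how long the subject tests positive. The SAP 13.3 overall formula is wrong whichever reading is taken, since it gives 200% for full adherence.

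The effect is confined to deviation reporting, the compliance summary and possibly the PP sensitivity analyses. Its frequency and direction cannot be estimated from the documents. The primary analysis uses the ITT set and does not change. This should be corrected before database lock, but it is not a threat to the main conclusion. No view is taken on the hold and reduction rules themselves.

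**What to change.** In SAP 13.3, and for the inter-visit rate in Protocol 9.5, define:

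compliance (%) = tablets taken / tablets prescribed × 100, where tablets prescribed = 2 × days in the period, less tablets withheld or reduced under Table 2.

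This gives 100% for full adherence and 42/42 = 100% for the worked case. State which visits bound an interval.

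Reconcile 9.5 with 8.5 by stating that holds and reductions made under Table 2 are not compliance deviations and do not by themselves exclude a subject from the PP set. Carry this into the sponsor's blinded definition of major deviations under SAP 11.6.

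The data should largely exist: interruptions are on the IP Interruptions CRF page (SAP 13.3), dose reductions appear as an action taken on the adverse event CRF (SAP 13.5.8.1), and Protocol 9.5 requires all dosing to be documented in the eCRF. The sponsor should confirm that start and stop dates of reductions were captured.

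The cost is a few sentences, one extra derivation and a blinded reclassification of compliance deviations already logged. No hold or reduction rule changes.

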9.6. Concomitant Medications

Any medication or vaccine (including over-the-counter or prescription medicines, vitamins, and/or herbal supplements) that the subject receives from the time of ICF signing through the end of the study must be recorded along with the following:

- Reason for use
- Dates and timing of administration, including start date/time and stop date/time
- Dose and frequency of administration

Subjects receiving HU must have received it continuously for at least 6 months prior to signing the ICF, and must have been on a stable dose for at least 3 months prior to signing the ICF, with no anticipated need for dose adjustments during the study including the screening period, in the opinion of the investigator.

Over-the-counter medications such as analgesics and nonsteroidal anti-inflammatory drugs that are taken on an as-needed basis can be continued as long as they are not medications that interfere with metabolism, transport, or assessments (refer to [Appendix 1](#) for additional information). All concomitant medications and/or therapies must be recorded on the appropriate pages of the eCRF. Use of any prohibited medication and/or therapy must also be recorded on the eCRF and must be documented as a protocol deviation.

9.6.1. Non-investigational Medicinal Products

Not applicable.

9.6.2. Prohibited Concomitant Medications/Therapies

The investigator, in consultation with the medical monitor, will determine if any of the following concomitant medications/therapies are necessary for the well-being of the subject. The subject will be withdrawn from the study if the following are determined to be necessary:

- PDE5 inhibitors; any drugs or substances, including grapefruit juice or herbal supplements with CYP altering properties, that are known to strongly or moderately inhibit or induce CYP3A enzymes; and any drugs or substances that are substrates or inhibitors of P-gp or BCRP. Sensitive substrates of CYP3A4/5 are also prohibited. If there is any question as to whether a substance is permitted, please review the product labeling (if applicable) and consult the medical monitor and/or sponsor.

- Previous use (within 6 months prior to signing the ICF) or concomitant use of erythropoietin, luspatercept (Reblozyl®), or other erythropoiesis-stimulating or erythroid maturation agent.
- Previous use (within 6 months prior to signing the ICF) or concomitant use of crizanlizumab (Adakveo®) or voxelotor (Oxbryta®).
- Any other investigational drug or device.

Because IMR-687 is a CYP3A4 substrate as well as a possible CYP3A4 inducer, caution should be employed in the co-administration of IMR-687 with other medications that are known CYP3A4 substrates. This potentially helps manage the competition for in vivo CYP3A4-mediated clearance, which could result in a DDI. This approach includes applying caution with dosing other oral medications to minimize the chance of a drug interaction at the site of absorption (e.g., the GI tract). Additional information on potential drug interactions and how to proceed can be found in Section [5.2.3](#).

Medications prohibited prior to study entry are described in the exclusion criteria in Section [8.2](#).

9.6.3. Prohibited Concomitant Procedures

Procedures prohibited prior to study entry are described in the exclusion criteria in Section [8.2](#).

If a subject requires a blood transfusion at the Day 1 or Week 4 visit, the medical monitor should be notified, and the visit will be rescheduled while the subject proceeds with the transfusion. If a subject requires a blood transfusion during the study, the subject may continue to receive study drug and participate in the study.

9.7. Handling and Disposal

At the end of the study, a final reconciliation must be made between the quantity of study drug supplied, dispensed, and subsequently returned to the sponsor. A written explanation must be provided for any discrepancies. After accountability has been performed by the sponsor or sponsor's designee, any unused study drug remaining at the end of the study will be returned to the sponsor for destruction. On-site destruction of unused study drug will be permitted with prior notice and approval from the sponsor.

